#### **8.2.6.1. Local and Central Laboratory Assessments**

The laboratory assessments for safety and establishing eligibility will be performed at local laboratories at the time points noted in Section 1.3 (SoA). The Screening Local laboratory results from Screening will be entered into the EDC system by the sites. All assessments from Day 0 to 180/ET will be performed by the central laboratory; those for Screening will be done by a local laboratory.

The Investigator must review the laboratory report, document this review, and record any clinically relevant changes occurring during the study. The laboratory reports must be filed with

---

the source documents and uploaded into the EDC. Clinically significant abnormal laboratory findings are those that are not associated with the underlying disease, unless judged by the Investigator to be more severe than expected for the Participant's condition.

All protocol-required laboratory assessments must be performed in accordance with the laboratory manual and the SoA.

#### **8.2.6.1.1. Hematology**

- White blood cell count
- Neutrophil (including calculated absolute neutrophil count)
- Hemoglobin
- Hematocrit
- Platelet count

#### **8.2.6.1.2. Kidney Function Tests**

- Blood urea nitrogen (BUN)
- Creatinine

#### **8.2.6.1.3. Liver Function Tests**

- Aspartate aminotransferase (AST)
- Alanine aminotransferase (ALT)
- Alkaline phosphatase
- Gamma-glutamyl transpeptidase (GGT)
- Total bilirubin
- Total protein
- Albumin

#### **8.2.6.1.4. Clinical Chemistry**

- Electrolytes (sodium, potassium, chloride, bicarbonate, calcium, inorganic phosphate, magnesium)
- Glucose (random collection, i.e., not necessarily fasting)
- Amylase
- Lipase
- Lactate dehydrogenase
- Creatine kinase

---

**8.2.6.1.5. Additional Tests**

- Urine pregnancy test

**8.2.6.1.6. Viral Screening**

- HIV
- HTLV I/II antibody with reflex confirmatory assay
- HBcAb (IgM)
- HBsAb
- HBsAg
- HBV viral load (if needed clinically)
- Anti-HCV antibodies and a positive qualitative PCR to assess HCV viral load

**8.2.7. Slow Vital Capacity**

Slow vital capacity is a pulmonary function test that quantifies the volume of air that can be slowly exhaled after slow maximum inhalation. SVC will be determined at Screening, predose on Days 60 and 120, and on Days 30, 84, 144, and 180/ET.

**8.3. Other Assessments and Procedures****8.3.1. Revised Amyotrophic Lateral Sclerosis Functional Rating**

The revised Amyotrophic Lateral Sclerosis Functional Rating Scale (ALSFRS-R) is a validated rating scale for measuring the global function of patients with ALS. It provides a health professional-generated estimate of the patient's degree of functional impairment, which can be evaluated serially to objectively assess any response to treatment or progression of disease. The ALSFRS-R includes twelve questions that ask the physician to rate his/her impression of the patient's level of functional impairment in performing one of twelve common tasks, e.g., climbing stairs. Each task is rated on a five-point scale from 0 (can't do) to 4 (normal ability). Individual item scores are summed to produce a reported score of between 0=worst and 48=best. The ALSFRS-R will be conducted at Screening, predose on Days 0, 60, and 120, and on Days 30, 84, 144, and 180/ET. Details about the scale can be found in Section 10.6, Appendix 6.

**8.3.2. Handheld Dynamometry**

Muscle strength will be measured quantitatively by Handheld Dynamometry (HHD) and the change from baseline in HHD following Engensis injections as compared to Placebo. HHD is a procedure by which a dynamometer is applied to the body of an individual being tested.

A non-AC powered dynamometer (manufactured by Hoggan Health Industries, Inc) will be used at all clinical sites. These measurements will be performed predose on Days 0, 60, and 120, and on Days 30, 84, 144, and 180/ET. Strength measurements will be evaluated by individual muscles.

---

**8.3.3. Accurate Test of Limb Isometric Strength**

The Accurate Test of Limb Isometric Strength (ATLIS) is designed to evaluate muscle strength and measure the isometric strength of 12 muscle groups in the arms and legs and will be conducted at clinical sites that have ATLIS available and staff trained and available to administer the strength evaluation. ATLIS will be measured predose on Days 0, 60, and 120, and at Visits on Days 30, 84, 144, and 180/ET

**8.3.4. Muscle Biopsies**

Helixmith intends to use muscle biopsy samples of the gastrocnemius to evaluate biomarkers in order to gain further understanding of Engensis' mechanism of action and muscle atrophy in ALS. Testing results could provide information for future uses of Engensis in ALS. A biopsy of the gastrocnemius will be collected (and stored) at Day 0 predose, and on Days 84 (optional) and 144. See the Muscle Biopsy Guidelines for detailed information on the techniques and procedures to be used.

**8.3.5. Quality of Life Assessment, Patient Reported Outcomes, and Clinical Reported Outcomes****8.3.5.1. Amyotrophic Lateral Sclerosis Assessment Questionnaire**

The Amyotrophic Lateral Sclerosis Assessment Questionnaire (ALSAQ-40) is a disease-specific, Participant self-report health status, or electronic patient-reported outcome (ePRO). There are 40 questions in the ALSAQ-40 with 5 discrete scales: physical mobility (10 questions), activities of daily living and independence (10 questions), eating and drinking (3 questions), communication (7 questions), and emotional reactions (10 questions). The ALSAQ-40 will be measured predose on Day 0 and at Visits on Days 84 and 180/ET. See Section 10.7, Appendix 7, for the ALSAQ-40 questionnaire.

Participants are asked to think about the difficulties that they may have experienced during the last two weeks (e.g., "I have found it difficult to feed myself"). Participants are asked to indicate the frequency of each event by selecting one of 5 options (Likert scale): never, rarely, sometimes, often, always, or cannot do at all.

**8.3.5.2. Patient Global Impression of Change**

The Participant's impression of change after treatment will be measured with the Patient Global Impression of Change (PGIC) questionnaire through use of the ePRO. This questionnaire measures the Participant's perception of how treatment has affected their level of activity, symptoms, emotions, and overall quality of life. Each descriptor is ranked on an intensity scale of 1 = Very Much Improved; 2 = Much Improved; 3 = Minimally Improved; 4 = No Change; 5 = Minimally Worse; 6 = Much Worse; 7 = Very Much Worse. The test will be self-administered during the Days 84 and 180/ET Visits. The PGIC questionnaire is presented in Section 10.8, Appendix 8.

---

Upon completion of the questionnaire, the study coordinator will check the questionnaire for completeness. Any omissions or ambiguous answers will be clarified by the Participant prior to leaving the clinic.

### **8.3.5.3. Clinical Global Impression of Change**

The Clinical Global Impression of Change (CGIC) is a validated instrument completed by observers as an assessment of QoL. The CGIC is a 7-point scale with scores range from 1 (very much improved) through 7 (very much worse). The test will be self-administered during the Days 84 and 180/ET Visits. The CGIC questionnaire is presented in Section [10.8](#), Appendix 8.

## **8.4. Blood Samples Stored for Future Genetic Testing**

Blood samples will be collected from all Participants to be stored for future genetic testing at Screening.

## **8.5. Adverse Events and Serious Adverse Events**

The definitions of AEs, TEAEs, SAEs and TESAEs can be found in Section [10.2](#), Appendix 2.

### **8.5.1. Time Period and Frequency for Collecting AE, TEAE, SAE, TESAE Information**

All study-related AEs and SAEs will be collected starting after completion of the informed consent process at Screening to Day 0/randomization. TEAEs and TESAEs will be collected after first injections on Day 0 through Day 180/ET or the last Study Visit up until the time that the Participant withdraws consent. (see definition of TEAE, Section [10.2](#)). Any SAE occurring after consent and before the first injection on Day 0 should be recorded and reported only if associated with a protocol-specified procedure. Any AEs reported during Screening after completion of informed consent will be collected and recorded separately from TEAEs reported on Day 0 and through the end of the study.

Medical occurrences that begin before the start of study intervention and not related to required study procedures, but after obtaining informed consent will be recorded on the Medical History/Current Medical Conditions section of the eCRF and not as AEs.

All SAEs will be recorded and reported to the Sponsor or designee immediately and under no circumstance should this exceed 24 hours, as indicated in Section [10.2.6](#), Appendix 2. The Investigator will submit any updated SAE data to the Sponsor within 24 hours of its availability.

Investigators are not obligated to actively seek AEs or SAEs after conclusion of the study participation. However, if the Investigator learns of any SAE, including a death, at any time after a Participant has been discharged from the study, and he/she considers the event to be possibly, probably, or definitely related to the study intervention or study participation, the Investigator must promptly notify the Sponsor.

---

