**FOOTNOTES FOR THE SCHEDULE OF ACTIVITIES**

**Note:** The Schedule of Activities includes activities during Screening and all Study Visits.

**Order of Assessments during Visits (if assessment is to be performed):** AEs/TEAEs, vital signs and weight, ALSFRS-R, HHD, ATLIS, pregnancy test, complete physical exam, SVC, ALSAQ-40, other questionnaires (PGIC and CGIC), blood sample collection for laboratory assessments, and muscle biopsy

- a Day 0 is the Baseline Visit
- b The Day 14 Visit will be scheduled 13-15 days after the Day 0 Visit, the Day 74 Visit will be scheduled 13-15 days after the Day 60 Visit, and the Day 134 Visit will be scheduled 13-15 days after the Day 120 Visit
- c Muscle biopsies will be collected as the last procedure of the Visit. It is collected predose on Day 0.
- d Day 84 muscle biopsy is optional.

**Abbreviations:** AEs = adverse events; AESI = adverse events of special interest; ALSFRS-R = Revised Amyotrophic Lateral Sclerosis Functional Rating Scale; ALSAQ-40 = Amyotrophic Lateral Sclerosis Assessment Questionnaire, 40 questions; ATLIS = accurate test of limb isometric strength; CGIC = Clinical Global Impression of Change; D = day; ET = early termination or withdrawal; HHD = Handheld Dynamometry; PGIC = Patient Global Impression of Change; SVC = Slow Vital Capacity; TEAEs = treatment-emergent adverse events; TESAEs = treatment-emergent serious adverse events

1. **Informed Consent** process is to be completed at Screening prior to conducting any study-specific procedures.
2. **Demographics and Baseline Characteristics** will include age, gender, race, and ethnicity and will be collected at Screening.
3. **Medical History and Familial Cancer History:** A medical history and familial cancer history will be obtained at Screening. The Investigator will confirm the diagnosis of ALS using the revised El Escorial / Airlie House diagnostic criteria. Participants will be confirmed as having clinically definite ALS, clinically probable ALS, or clinically probable laboratory-supported ALS  $\leq 4$  years.

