## 2. INTRODUCTION

Engensis is a novel gene therapy being developed for treatment of ALS. The active pharmaceutical ingredient of Engensis is VM202 (donaperminogene seltoplasmid), a plasmid deoxyribonucleic acid (DNA) designed as a gene transfer method to simultaneously express two isoforms of human hepatocyte growth factor (HGF), HGF728 and HGF723, that are identical to wild-type human forms.

Hepatocyte growth factor is a potent angiogenic and vasculogenic growth factor stimulating the growth of endothelial cells and migration of vascular smooth muscle cells. As a multifunctional mesenchyme-derived cytokine, it has potent angiogenic and anti-apoptotic effects, including that of the lymphatic system. In addition, HGF upregulates the expression of vascular endothelial growth factor (VEGF) and other factors and demonstrates greater mitogenic activity than that of VEGF alone in human aortic endothelial cells in vitro. HGF is also important in the pathophysiology of insulin resistance, as a neurotrophic factor promoting axonal growth and regeneration in diabetics in whom loss of microvasculature may accelerate neuronal loss, more so than exogenous VEGF (see the Investigator's Brochure [IB] for more detailed information).

In this study Engensis will be administered by IM injection, which has distinct advantages over alternative delivery modes of HGF or Engensis. Intravenous infusion is impeded by rapid clearance of HGF by the liver and of Engensis by DNases, resulting in low tissue levels. The VM202 plasmid DNA expresses HGF in situ, allowing local targeted delivery. Plasmid DNA also has a lowered risk of genomic integration and of generating immune responses compared with viral delivery systems. Importantly, certain components of Engensis, including its unique plasmid vector pCK and promoters and controllers of gene transcription that make the expression from skeletal muscle more efficient (see the IB for full description), lead to expression of HGF that is detectable for up to 30 days after direct skeletal muscle injection.

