**4.4. Justification for Dose**

Pharmacokinetic studies in animals and humans both indicate that VM202 (Engensis) has very limited systemic distribution. The plasmid DNA product is taken up into muscle cells within a radius of about 1 cm of each IM injection site. Only a small fraction of VM202 DNA is detectable in the systemic circulation following IM injection. VM202's short circulatory half is 2 to 5 minutes consequent to rapid clearance by circulating DNases and rapid uptake by the liver (reference Investigator's Brochure). The expression of human HGF after intracellular VM202 uptake continues for about 2 to 3 weeks following injection (*ibid.*). As HGF protein can bind to heparan sulfate, which is abundant in the extracellular matrix (ECM), longer-term retention of HGF protein results from entrapment within the ECM. Most HGF released into circulation, including from the ECM, is quickly degraded. The repeated injection of Engensis in study VMALS-002-2, with 6 treatment days over 19 weeks, is thus expected to provide enhanced HGF expression for approximately 5 to 6 months.

In addition, the favorable safety profile of Engensis from 10 clinical studies with over 500 total Participants who have received the drug indicates that the minimal safety risk of 3 cycles of treatment with Engensis over a 19-week period is justified for Participants with a life-threatening illness who may receive a potential benefit from increased neuromuscular activity and greater ability to exert self-control of voluntary muscle movements during their participation in study VMALS-002-2.

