## 7. DISCONTINUATION OF STUDY INTERVENTION AND PARTICIPANT WITHDRAWAL

### 7.1. Discontinuation of Study Intervention

In rare instances, it may be necessary to discontinue study drug for a Participant. If study drug is discontinued, the Participant will remain in the study to be evaluated for safety if the Participant agrees to continue participating in the study. See Section 1.3 (SoA) for any further assessments that need to be completed.

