6.14.1 Adverse Events

All study-related Adverse Events (AEs) will be collected starting after completion of the informed consent process at Screening to Day 0/randomization. Treatment-Emergent Adverse Events (TEAEs) and Treatment-Emergent Serious Adverse Events (TESAEs) will be collected after first injections on Day 0 through Day 180/End of Treatment or the last Study Visit up until the time that the Participant withdraws consent. All Serious Adverse Events (SAEs) will be collected from the completion of the informed consent process until Study Day 180 or the last Study Visit up until the time that the Participant withdraws consent. Any SAE occurring after consent and before the first injection on Day 0 should be recorded and reported only if associated with a protocol-specified procedure. Any AEs reported during Screening after completion of informed consent will be collected and recorded separately from TEAEs reported on Day 0 and through the end of the study.

Medical occurrences that begin before the start of study intervention and not related to required study procedures, but after obtaining informed consent will be recorded on the Medical History/Current Medical Conditions section of the eCRF and not as AEs.

Adverse events with relationship equal to “Possibly related”, “Probably related” and “Definitely related” will be considered as adverse events related to study medication. If an AE has missing relationship it is assumed to be related to the study drug for analysis purposes.

Adverse events with fatal outcome will be considered as fatal events. Maximum severity will be assumed for an AE with missing severity.

AEs will be coded using Medical Dictionary of Regulated Activities (MedDRA, version 23.0, or later) by System Organ Class (SOC) and preferred term (PT).

Adverse Event (AE) Definition

- An AE is any untoward medical occurrence in a patient or clinical study Participant, temporally associated with the use of study intervention, whether or not considered related to the study intervention.
- NOTE: An AE can therefore be any unfavorable and unintended sign (including an abnormal laboratory finding), symptom, or disease (new or exacerbated) temporally associated with the use of study intervention.

Treatment-Emergent Adverse Event (TEAE) Definition

QMD Ref: Worldwide-TMP-ST-005-7.0 Effective: 12Aug2019	Governing QMD: Worldwide-SOP-ST-001
Confidentiality Statement	

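### For a participant who leaves early, collection of new TEAEs can end 0 to 16 days after the last injection, short of the 3 weeks to 30 days of HGF expression that the protocol describes

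*Protocol*

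**What the plan says.** Protocol 8.5.1 sets the collection period for the primary safety endpoint: "TEAEs and TESAEs will be collected after first injections on Day 0 through Day 180/ET or the last Study Visit", up to withdrawal of consent. After that, "Investigators are not obligated to actively seek AEs or SAEs after conclusion of the study participation". A site that happens to learn of a later SAE must report it only if the investigator considers it related.

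The protocol is clear about what ET means: "ET = early termination or withdrawal" (footnotes to the Schedule of Activities). Section 7.2 asks for an ET visit if one is possible, lists TEAEs among its assessments, and gives no timing relative to the last injection. Section 8.5.5 requires follow-up, but of SAEs and AESIs already reported. The one contact scheduled between visits, 2 to 3 days after each injection visit, asks about injection site reactions.

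Stopping the drug is a different matter from leaving the study. Section 7.1 says: "If study drug is discontinued, the Participant will remain in the study to be evaluated for safety", if the participant agrees.

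On duration of drug action, Protocol 4.4 says: "The expression of human HGF after intracellular VM202 uptake continues for about 2 to 3 weeks following injection". Protocol Section 2 describes "expression of HGF that is detectable for up to 30 days after direct skeletal muscle injection".

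SAP 6.14.1 repeats the collection sentence with the abbreviation expanded differently: events "will be collected after first injections on Day 0 through Day 180/End of Treatment or the last Study Visit". The TEAE definition in the same SAP section runs from the first dosing day to the end of study.

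**The concern.** Safety is the only primary objective, and TEAE and TESAE incidence is a primary endpoint. The protocol itself says how long the product is expected to be active after an injection. The visit schedule covers that period for completers. For someone who exits between cycles or soon after an injection visit, nothing requires the site to ask about new events during the rest of it. A new non-serious TEAE or AESI in that interval has no route into the tables. An SAE has one only if the site hears of it and judges it related. Protocol 9.3.1 allows no imputation for the safety summaries, so the analysis cannot recover what was not collected.

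The exits for which this matters are those where consent stands, for example for an adverse event, by investigator decision or for non-compliance. In the first two, a safety question may already be open.

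The SAP's End of Treatment is a separate fault. It does not create the gap, which comes from the protocol sentence, but it names a different stopping point from the protocol's ET.

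**Working it through.** The plan gives no figure for minimum post-injection follow-up, so there is none to reproduce. As a check on the schedule, 134/7 = 19.1 weeks, which agrees with the 19 weeks in Protocol 4.4.

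**Inputs**
- Injection days 0, 14, 60, 74, 120 and 134 (Protocol 4.1).
- Visits without injections: Days 30, 84, 144 and 180/ET (Protocol 4.1).
- Visit windows: Day 120 ±3; the Day 134 visit 13 to 15 days after the Day 120 visit; Day 180 ±7 (Schedule of Activities and its footnotes).
- Expression about 14 to 21 days (4.4), detectable to 30 days (Section 2).
- Target arm sizes 12 and 6 (5.3).

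**Completers**
- Nominal: 180 − 134 = 46 days.
- Shortest within windows: latest second injection 120 + 3 + 15 = Day 138; earliest final visit 180 − 7 = Day 173; 173 − 138 = 35 days. Both 21 and 30 days are covered.

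**Early leavers whose last contact is a scheduled visit** (last visit minus latest injection, nominal days)
- Any injection day: 0.
- Day 30: 30 − 14 = 16.
- Day 84: 84 − 74 = 10. Day 144: 144 − 134 = 10.

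The 0 and 10 fall short of even two weeks. The 16 passes two weeks but not three weeks or 30 days.

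**Share of possible exit days, Days 0 to 179.** Within a cycle the injections are 14 days apart, so a period of w days after each injection covers 14 + w days per cycle when w is at least 14.

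| Period after an injection | Days covered | Share of 180 |
|---|---|---|
| 14 days | 3 × 28 = 84 | 47% |
| 21 days | 3 × 35 = 105 | 58% |
| 30 days | 3 × 44 = 132 | 73% |

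**Weight of one participant.** 1/12 = 8.3 percentage points on Engensis; 1/6 = 16.7 on Placebo. This applies to a measure on which that participant would otherwise count as event-free: a first TESAE, a first AESI or a first occurrence of a given preferred term.

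**Observation added by a 30-day contact.** 30 − 0 = 30 days for an exit on an injection day, 30 − 10 = 20 for Day 84 or 144, 30 − 16 = 14 for Day 30, and none for completers.

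**The case against.** The group affected is narrow. Participants who only stop the drug stay under observation if willing (7.1). Those who withdraw consent cannot be reached by any collection rule. Those who stop attending are pursued by telephone and certified letter before being declared lost (7.3). SAEs and AESIs already reported are followed (8.5.5). In the earlier ALS study, 17 of 18 participants completed nine months and the other died (2.2.6.1), so early exit may be rare. All of this stands, and it limits the size of the point. It does not supply observation for a consenting participant who exits, for example, at Day 84.

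Injection site reactions are barely touched, since they must appear within 48 hours (8.5.4.3) and are asked about at 2 to 3 days. That also stands.

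Neither expression figure is presented as a safety window, and 4.4 adds that HGF protein may be retained longer. So 30 days is a choice: it is the longest expression figure the protocol states.

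Four stronger readings are tempting and should not be drawn:
- **That the SAP closes the TEAE window when injections stop.** This would lose 180 − 14 = 166 days for someone who stops after Day 14 and stays on study. The clause goes on to the last Study Visit ("through Day 180/End of Treatment or the last Study Visit up until the time that the Participant withdraws consent"), the SAP's TEAE definition runs to the end of study, and SAP Section 9 declares no change from the protocol analysis. It is a wrongly expanded abbreviation.
- **That any missed event shifts TEAE incidence by 8.3 or 16.7 points.** Incidence counts participants. Someone already counted with a TEAE does not move the overall figure, and 94.4% of participants in the earlier ALS study had an AE (Synopsis).
- **That the bias favours Engensis.** The documents give no exit rates by arm and no delayed-event rates.
- **That 58% to 73% is a risk of missing events.** It is a share of calendar days, and it becomes a probability only for someone who exits, and only if exit times are uniform.

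**Conclusion.** The point holds as a gap in required observation. A consenting participant who leaves early need not be asked about new events beyond the ET visit or last visit, which at scheduled visits before Day 180 means 0, 10 or 16 days after the latest injection, against at least 35 for a completer. Need not be observed is the accurate wording: an ET visit could fall later, and a related SAE the site learns of must still be reported.

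The figures rest on nominal visit days, except the 35, and on target arms of 12 and 6. The number of participants affected cannot be estimated from the documents and may be none. If one is affected, the effect on the specific measures named above is 8.3 or 16.7 points; on overall TEAE incidence it is zero if that participant already has a TEAE. The direction of any bias is unknown.

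The SAP wording conflicts with the protocol's ET and with the SAP's own definition. It is an editorial correction, not a cause of the gap. The change is worth making because it is cheap and serves the primary endpoint, but the gap does not undermine the trial.

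**What to change.** **Protocol 7.2, 8.5.1 and the Schedule of Activities (ET column and footnotes).** For any participant who leaves the study within 30 days of the last injection and has not withdrawn consent, require one telephone contact to collect new TEAEs, TESAEs and AESIs through 30 days after that injection.

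**SAP 6.14.1.** Replace End of Treatment with Early Termination. Keep the TEAE definition that runs to the end of study, and add that events collected at this contact count as TEAEs. The addition is useful because SAP 6.2.14 keeps unscheduled and early termination assessments out of the tables, and a reader could extend that to these events.

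Do not define the SAP window as the later of the ET visit and 30 days after the last injection. That omits Day 180. A completer has no ET visit, so the window would end at 134 + 30 = Day 164, 16 days early. For someone who stops the drug after Day 14 and stays on study, it would end at 14 + 30 = Day 44.

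**Cost.** One call per early leaver and short text changes, with no added visit or sample and nothing extra for completers. The information rests on recall, and participants who refuse contact remain incomplete.
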